### 1.1. Objective

The aim of this study is to investigate the effect of hospitalisation due to acute illness on muscle mass characteristics, assessed in older adults through ultrasound. The primary endpoint is the change of characteristics of muscle mass in function of time since admission. The secondary endpoint of the study is to identify health related parameters associated with the development of acute sarcopenia. Relevant determinants of the evolution of muscle

mass and muscle strength since admission (reason of hospitalisation, comorbidities and laboratory data) will therefore also be investigated.

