## **2. Methods**

### **2.1. Study design**

A prospective, multicenter, international observational study will be conducted. The study is designed to determine the effect of hospitalisation due to acute illness on the changes in muscle mass and muscle function. The secondary endpoint of the study is to identify health related parameters associated with the development of acute sarcopenia.

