### 2.3.2. Muscle mass

In order to obtain reliable and consistent measurements, all ultrasonography will be done by an ultrasonographist that is trained to perform the measurements proposed. For the measurements, a linear probe of 5 cm width will be used. Frequency of the beam will be set on 12 MHz.

Patients should not have had any physical exercise in the 30 minutes before the measurement. Muscles should be completely relaxed and patients should be placed in the supine position, with hips in neutral position and knees fully extended. The dominant leg will be taken for the measurements. To calculate the relative muscle thickness values, the total length of muscle will be noted.

Ultrasonographic data of the four bellies of the quadriceps muscle (rectus femoris, vastus lateralis, vastus medialis, vastus intermedius) will be taken. Measuring points will be specified according to the propositions of the SARCUS-working group [19]. Muscle thickness, fascicle length, pennation angle, muscle cross-sectional area and echo-intensity of all muscles listed will be taken.

The first measurement will be taken as early as possible within 48 hours after admission at the latest. Follow-up measurements will be taken according to the type of ward the patient is admitted to. For patients that are expected to be hospitalized for a limited time (<5 days), the follow-up measurement will be done 3 days after initial measurement. For patients that are expected to be hospitalized for a longer time (>7 days), measurements will be repeated 7

days after initial measurement, to be repeated after another 7 days as long as the patient is hospitalized.

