### **2.3.3. Muscle strength and function**

Muscle strength will be measured through hand grip strength using a Jamar dynamometer, using the Southampton protocol [23]. The first measurement will be taken as early as possible within 48 hours after admission at the latest. Follow-up measurements will be taken according to the type of ward the patient is admitted to. For patients that are expected to be hospitalized for a limited time (<5 days), the follow-up measurement will be done 3 days after initial measurement. For patients that are expected to be hospitalized for a longer time (>7 days), measurements will be repeated 7 days after initial measurement, to be repeated after another 7 days as long as the patient is hospitalized. Measurement will be done directly after the ultrasonographic assessment. If feasible, muscle function will be measured through gait speed, using the 4-meter walking test at usual gait speed [24]. In case of those bedridden, gait speed will not be measured.

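### The follow-up schedule in sections 2.3.2 and 2.3.3 gives no timing for expected stays of 5 to 7 days, so the second measurement behind the primary change endpoint is undefined for that group

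*Combined protocol and SAP*

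**What the plan says.** The primary endpoint, in section 1.1, is a change over time: "The primary endpoint is the change of characteristics of muscle mass in function of time since admission". Section 2.1 adds muscle function: "The study is designed to determine the effect of hospitalisation due to acute illness on the changes in muscle mass and muscle function".

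Section 2.3.2 sets the timing of the ultrasound scans.
- Baseline: "The first measurement will be taken as early as possible within 48 hours after admission at the latest".
- General principle: "Follow-up measurements will be taken according to the type of ward the patient is admitted to".
- Short expected stay: "For patients that are expected to be hospitalized for a limited time (<5 days), the follow-up measurement will be done 3 days" after the first measurement.
- Long expected stay: "For patients that are expected to be hospitalized for a longer time (>7 days), measurements will be repeated 7" days after the first, then weekly until discharge.

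Section 2.3.3 repeats the same two bands for grip strength ("For patients that are expected to be hospitalized for a longer time (>7 days), measurements will be repeated 7 days after initial measurement") and ties grip to the scan: "Measurement will be done directly after the ultrasonographic assessment".

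Section 2.2.1 names four ward types: internal medicine, acute geriatrics, orthogeriatrics and rehabilitation. No section says which schedule any of them follows.

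**The concern.** The two bands are strict inequalities, below 5 days and above 7 days. A patient expected to stay 5, 6 or 7 days is in neither. A change endpoint needs at least two measurements, and for these patients the plan does not say when, or on a literal reading whether, the second one is due. Grip strength follows the scan and repeats the same bands, so it has the same hole.

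A scan that was not taken before discharge cannot be recovered at the analysis stage. If centres fill the hole in different ways, similar patients will contribute change data in one centre and not in another, and those who do contribute will have been measured at different times.

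**Working it through.** The plan states no figure on this point, so there is none to reproduce. The check is one of coverage and timing.

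**Step 1: coverage.** Expected stays with a rule: E < 5 or E > 7. The complement is 5 ≤ E ≤ 7, both ends included. Sections 2.3.2 and 2.3.3 leave the same interval open, and no other section closes it.

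**Step 2: does ward type close it?** Four wards are listed in section 2.2.1 and none is given a schedule. Two readings remain:
- Literal: no second measurement is scheduled for 5 ≤ E ≤ 7.
- Ward tracks: each patient is on the short or the long track, but the plan does not say which, so the second measurement is due at either +3 or +7 days.

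**Step 3: does the choice matter?** Let t be the time of the first scan in days since admission. Section 2.3.2 gives 0 ≤ t ≤ 2. Let L be the actual stay.
- +3 rule: second scan at t + 3, which is day 0 + 3 = 3 to day 2 + 3 = 5.
- +7 rule: second scan at t + 7, which is day 0 + 7 = 7 to day 2 + 7 = 9.

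For 5 ≤ L ≤ 7:
- t + 3 ≤ 5 ≤ L always holds, so the +3 scan falls within the stay or, at the latest, on its last day (L = 5, t = 2).
- t + 7 ≤ L requires t ≤ L − 7. As t cannot be negative, this holds only for L = 7 and t = 0.

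A +7 default therefore misses nearly every patient who actually stays 5 to 7 days, and a +3 default misses none of them. When the actual stay departs from the expectation, the picture softens: any L ≥ 9 reaches the +7 scan, any L < 3 misses the +3 scan, and stays of 3 to 5 days reach the +3 scan only if the first scan was early enough.

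**Step 4: how many patients?** The documents give no length-of-stay distribution and no sample size, so this cannot be computed. As an illustration only, assume a log-normal stay with median m and log-SD s, and expected stay equal to actual stay. Then P(5 ≤ E ≤ 7) = Φ[ln(7/m)/s] − Φ[ln(5/m)/s].
- m = 5, s = 0.6: Φ(0.561) − Φ(0) = 0.713 − 0.500 = 0.213.
- m = 12, s = 0.6: Φ(−0.898) − Φ(−1.459) = 0.184 − 0.072 = 0.112.
- m = 20, s = 0.6: Φ(−1.750) − Φ(−2.311) = 0.040 − 0.010 = 0.030.
- m = 20, s = 0.8: Φ(−1.312) − Φ(−1.733) = 0.095 − 0.042 = 0.053.

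Over medians of 5 to 12 days and s of 0.6 to 0.8 the share is about 11 to 21%. At a median of 20 days, which is conceivable where rehabilitation wards dominate, it is about 3 to 5%. The answer is driven by the assumption, and nothing below depends on it.

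**The case against.** The strongest reply is that the authors plainly meant everyone to be followed. The sentence on ward type introduces the bands, and the Discussion (section 3) counts frequent and regular re-measurement among the study's strengths. On that view the bands describe typical short-stay and long-stay settings, and only the day is unclear. This stands as a reading of intent. A reader might infer from the literal text that patients expected to stay 5 to 7 days cannot contribute change data at all. The documents do not support that, because a centre may reasonably place them on one of the two tracks. What does not stand is that the ward sentence supplies the day.

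A reader might also infer that patients in this group who go on to stay beyond 7 days are lost. That assumes expected stay is fixed at admission. If it is updated, they may enter the long-stay branch; the documents do not say which applies.

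Nor can it be said that every such patient is eligible on every reading. The Abstract's minimum of 5 days in hospital most naturally refers to actual stay, while the gap concerns expected stay, so some patients expected to stay 5 to 7 days could be discharged earlier and fall outside that criterion. Section 2.2.1 and Table 1 set no length-of-stay limit.

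Finally, patients in the two defined bands still yield change data, and a small edit repairs the text. That argues against the highest severity, but not against making the edit.

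**Conclusion.** The gap is real and appears in both measurement sections. For expected stays of 5 to 7 days the plan does not define the second ultrasound or the second grip measurement, and the ward sentence does not resolve it. The consequence is a risk that inclusion in the primary change analysis, and the time at which change is measured, depend on each centre's improvisation. A default of +7 days would lose nearly all patients who actually stay 5 to 7 days. That result rests only on the plan's own 0 to 48 hour window and the two intervals it names.

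The number of patients affected cannot be derived from the documents, and the direction of any bias is unknown. A reader might take the gap to mean that the primary result is biased or that a known fraction of patients is lost; neither follows. Severity: should be fixed.

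**What to change.** 1. Reword sections 2.3.2 and 2.3.3 so that the research measurement schedule covers every expected stay. One option among several is to apply the existing +3-day measurement to expected stays up to and including 7 days, with the existing weekly schedule if the stay extends. The choice of day is the investigators'; what matters is that no interval is left open.
2. State whether expected stay is fixed at admission or updated and, if updated, what happens to the schedule.
3. Either assign a schedule to each of the four wards or delete the ward sentence in both sections.
4. Because intervals will differ between patients, analyse change by actual days since admission with a model that accounts for repeated measurements within patient, for example a mixed model with a random patient effect. The tests that section 2.4 names for further analysis (Chi Square, Fisher exact, Mann-Whitney U) do not model within-patient change over time.

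Cost: a few sentences in two sections, one extra scan and grip set for these patients with equipment already in use, and one added analysis. Under the example in item 1, intervals become shorter and more variable, and 3 days leaves less time for change than 7. Modelling actual time handles unequal spacing but does not recover patients discharged before their second scan.

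Separately, the Abstract (at least 5 days in hospital), section 2.2.1 and Table 1 (no length-of-stay criterion) and sections 2.3.2 and 2.3.3 (a rule for expected stays under 5 days) must be reconciled on minimum stay. This point does not rest on how that is settled.

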## Abstract

Sarcopenia is a geriatric syndrome defined as progressive and generalized age-related muscle loss with decline in muscle mass and muscle function (either strength or performance). It is closely related to adverse outcomes such as frailty, reduced quality of life, increased risk of falling, more frequent hospitalisations and higher mortality. Acute sarcopenia is the decline of muscle mass and function following acute disease or hospitalisation, sufficiently to meet the criteria of sarcopenia.

Objectives: To assess the effect of hospitalisation and acute illness on muscle mass and function, and to assess which other factors contribute to the development of acute sarcopenia.

Study design and main outcome measures: This study is a prospective multicenter observational study. Patients admitted to acute geriatric wards of different European centers and hospitalised for at least 5 days will be included. Measurements of muscle mass will be performed via ultrasound. Measurements of muscle function will be done by hand grip strength using Jamar dynamometer and by gait speed using the 4-meter walking test, when feasible. Other parameters will be measured via file study, laboratory investigations or validated questionnaires. Activity levels during hospitalisation will be measured through pedometers.

Anticipated results: Decline of muscle mass and muscle characteristics secondary to hospitalisation. We also expect an association with reasons of hospitalisation, pre-existing conditions, laboratory results and nutritional status prior to hospitalisation on the decline in muscle parameters.

Conclusions: This study seeks to gain knowledge of the development of acute sarcopenia and its contributing factors.

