### **2.2. Subjects**

#### **2.2.1. Inclusion criteria**

Patients admitted between the 1st of November 2018 until the 31th of October 2019 will be eligible for inclusion. Included wards for admission are: internal medicine, acute geriatrics, orthogeriatrics and rehabilitation. Age limit will be set on 65 years and older.

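### Follow-up is timed from a baseline up to 48 h after admission and no discharge measurement is planned, so patients who leave before the scheduled day have no primary endpoint

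*Combined protocol and SAP*

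**What the plan says.** Section 1.1 defines the outcome: "The primary endpoint is the change of characteristics of muscle mass in function of time since admission". A patient contributes a change only with a baseline scan and at least one later scan.

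Section 2.3.2 sets the baseline: "The first measurement will be taken as early as possible within 48 hours after admission at the latest". Follow-up then depends on the expected stay. If that is under 5 days, "the follow-up measurement will be done 3 days after initial measurement". If it is over 7 days, the scan comes 7 days after the first one, "to be repeated after another 7 days as long as the patient is hospitalized". Section 2.3.3 gives grip strength the same schedule.

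Section 2.3.1 records the dates of admission and discharge, but nothing ties a measurement to discharge, and no post-discharge visit is described. Section 2.4 lists chi-square, Fisher exact and Mann-Whitney tests. It has no method for repeated measurements and no rule for a patient with only a baseline.

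On minimum stay the document is inconsistent. The Abstract says that patients "hospitalised for at least 5 days will be included". Section 2.2.1 and Table 1 give admission dates and age (2.2.1 also gives wards) but no minimum stay, and sections 2.3.2 and 2.3.3 provide a schedule for expected stays under 5 days.

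**The concern.** The clock for follow-up starts at the baseline scan, whereas the opportunity to scan ends at discharge. Every hour of delay before the baseline pushes the follow-up an hour closer to, or past, the day the patient leaves. With no measurement brought forward to discharge, patients whose stay ends first drop out of the primary endpoint, and out of the grip-strength change as well.

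This loss is not random: within each group it falls on the shorter stays. Length of stay is plausibly related to illness severity and inflammation, which the study wants to examine as determinants of muscle loss (sections 1.1 and 1.2). Both the primary estimate and the risk-factor comparisons are exposed, and a scan missed at discharge cannot be obtained later.

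This is separate from the absence of any schedule for expected stays of 5 to 7 days. Here the two schedules that are stated cannot be completed for some of the patients they cover.

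**Working it through.** The plan states no sample size, dropout rate or length-of-stay figure, so there is no figure of its own to reproduce. The check is timing arithmetic.

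**Inputs from the documents**
- Baseline time after admission, b: 0 to 2 days (section 2.3.2).
- First follow-up: b + 3 days for expected stay <5 days, b + 7 days for expected stay >7 days (sections 2.3.2 and 2.3.3).

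**Without assumptions.** With actual stay L, the follow-up is possible in hospital only if b + 3 ≤ L, or b + 7 ≤ L.
- The windows are 0 + 3 to 2 + 3 = day 3 to 5, and 0 + 7 to 2 + 7 = day 7 to 9.
- Long-stay group: an 8-day stay keeps its scan only if b ≤ 8 − 7 = 1 day (24 h). From a 9-day stay onward it is always possible. A patient who leaves before day 7 never has it.
- Short-stay group, if there is no minimum stay: a 4-day stay needs b ≤ 4 − 3 = 1 day, a 3.5-day stay needs b ≤ 12 h, and a stay under 3 days never has the scan.
- Short-stay group, if the Abstract's minimum governs: L ≥ 5 and b + 3 ≤ 5, so the scan is always possible.

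**With assumptions.** Take b uniform on 0 to B days, independent of stay, and stay uniform from 3 (or 7) days over a range of width w ≥ B. Then

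share missed = E[b] / w = (B/2) / w.

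| Assumed actual stay | w (days) | Baseline 0–48 h (B = 2) | Baseline 0–24 h (B = 1) |
|---|---|---|---|
| 3–5 days, +3 scan | 2 | 1/2 = 50% | 0.5/2 = 25% |
| 7–9 days, +7 scan | 2 | 1/2 = 50% | 0.5/2 = 25% |
| 7–10 days, +7 scan | 3 | 1/3 = 33% | 0.5/3 = 17% |
| 7–14 days, +7 scan | 7 | 1/7 = 14% | 0.5/7 = 7% |
| 7–21 days, +7 scan | 14 | 1/14 = 7% | 0.5/14 = 4% |

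The 3–5 day row applies only if there is no minimum stay. The long-stay rows start at 7 days, so they leave out patients expected to stay longer who go home before day 7; all of those lose the scan in addition.

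**Who is lost.** By simulation with baseline over 0–48 h, mean stay is 3.7 days in the missed against 4.3 days in the kept for stays of 3–5 days, and 7.7 against 11.0 days for stays of 7–14 days.

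**The case against.** Four points on the other side carry weight.

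1. **Minimum stay.** Under the Abstract's rule of at least 5 days, the +3-day scan can never fall after discharge. This stands. The short-stay part is conditional until the Abstract is reconciled with section 2.2.1, Table 1 and sections 2.3.2 and 2.3.3. The +7-day part is unaffected.

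2. **Expected is not actual stay.** A reader might infer that a baseline at 48 h loses the whole short-stay group, because day 5 lies outside a stay under 5 days. The groups are formed on expected stay, and some of these patients will stay longer. The inference holds only for actual stays under 5 days.

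3. **Size.** A reader might infer that about half of all patients lose the endpoint. The 50% belongs to stays of 3–5 or 7–9 days, the windows in which baseline delay decides the matter. The long-stay group has no upper limit, the plan foresees further weekly repeats, and section 2.2.1 includes orthogeriatric and rehabilitation wards. The wider ranges, with 14% and 7%, are therefore just as relevant. The plan also asks for the baseline as early as possible, which favours the lower column of figures.

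4. **Direction.** It is tempting to conclude that muscle loss will be overstated because quick recoverers are missing. Early death and transfer remove scans too, and patients who die may have lost the most muscle. The documents contain no data on stay, mortality or muscle change from which to settle this.

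It can also be said that the restriction to the hospital stay is written only for the weekly repeats. That is correct; for the first follow-up it is inferred from the absence of any later visit. If the sponsor intends outpatient scans, the plan needs to say so.

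**Conclusion.** The point holds in limited form. As written, any long-stay patient whose actual stay ends before baseline + 7 days has no primary endpoint, whichever minimum stay applies. The same is true at baseline + 3 days in the short-stay group only if the Methods text without a minimum stay governs.

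The size depends on a length-of-stay distribution that the documents do not give. Under the uniform assumptions above it runs from about 50% for the narrowest stay ranges to 7% for stays of 7–21 days, and from 25% to 4% if baselines are completed within 24 h. Earlier-than-expected discharges add to the long-stay figures.

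The loss falls on shorter stays and so is probably informative. Neither the amount nor the sign of the resulting bias can be derived from the documents. The case for changing the plan rests on cheaply keeping endpoint data that cannot be recovered afterwards, not on a demonstrated bias in one direction.

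**What to change.** First reconcile the minimum stay in the Abstract with section 2.2.1, Table 1 and the under-5-day schedule in sections 2.3.2 and 2.3.3.

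Then:
- In 2.3.2 and 2.3.3, take the first follow-up scan and grip test on the scheduled day or at discharge, whichever comes first.
- Record the date and time of admission and of each measurement.
- Record the reason for any missing second measurement (discharge, death, transfer, refusal or other), and report numbers and baseline characteristics of patients with and without it.
- In 2.4, analyse change against actual elapsed time, or as a rate per day, so that unequal intervals do not distort comparisons. A rate assumes roughly constant loss over the interval, which should be stated.

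The cost is wording in three sections and some coordination with discharge planning; the scan is brought forward, not added. Intervals will vary more, and the expected change will be smaller in patients discharged early. Because the interval then depends on the stay, comparing raw changes without regard to time would exchange one distortion for another, so the analysis change belongs with the scheduling change. Scans lost to death or sudden transfer will remain missing, which is why the reasons are needed.

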### **2.3.3. Muscle strength and function**

Muscle strength will be measured through hand grip strength using a Jamar dynamometer, using the Southampton protocol [23]. The first measurement will be taken as early as possible within 48 hours after admission at the latest. Follow-up measurements will be taken according to the type of ward the patient is admitted to. For patients that are expected to be hospitalized for a limited time (<5 days), the follow-up measurement will be done 3 days after initial measurement. For patients that are expected to be hospitalized for a longer time (>7 days), measurements will be repeated 7 days after initial measurement, to be repeated after another 7 days as long as the patient is hospitalized. Measurement will be done directly after the ultrasonographic assessment. If feasible, muscle function will be measured through gait speed, using the 4-meter walking test at usual gait speed [24]. In case of those bedridden, gait speed will not be measured.

